### 7.2.1 Multiple Imputation

When the primary outcome is unable to be derived due to missing data, multiple imputation will be used. This method will be applied to the components of the overall MVS: Diarrhea duration, Maximum number of diarrheal stools/24 hours, Vomiting duration, Maximum number of vomiting episodes/24 hours, Maximum fever, Unscheduled ED visit, Unscheduled Primary Care Visit, Rehydration, and Hospital Admission. In the case where no MVS outcome data are available, the subject will not be included in imputations and the outcomes will remain missing.

**Sequential Regression Multivariate Imputation Models** We will use logistic regression methods to model unscheduled ED visit, Unscheduled Primary Care Visit, Rehydration, and Hospital Admission. We will use Poisson or linear regression methods to model Diarrhea duration, Maximum number of diarrheal stools/24 hours, Vomiting duration, Maximum number of vomiting episodes/24 hours, and Maximum fever. For all models, we will use forward stepwise variable selection to select predictors.

**Variables to include in imputation models** *Stratum:* Stratify models using treatment assigned

*Minimum and maximum possible values will be computed and used as bounds for imputing MVS components:* Diarrhea duration, Maximum number of diarrheal stools/24 hours, Vomiting duration, Maximum number of vomiting episodes/24 hours, Maximum fever

*General model variables:* age, gender, breast-feeding status, hospital/site

*Baseline model variables:* duration of symptoms prior to enrollment, diarrhea duration, maximum number of diarrheal stools/24 hours, vomiting duration, maximum number of vomiting episodes/24 hours, maximum fever, dehydration status, antibiotics use, Number in household, number infected in household

*Post-randomization model variables:* Time to symptom resolution, ED disposition, primary care visits, Emergency department visits, hospital admissions, daycare days missed, work days missed, antibiotic use, invasive LGG disease, bloating, gas, intestinal rumbling, blood in stool, abdominal cramps, nausea, loss of appetite, heartburn, constipation, skin rash, muscle aches, sore throat, cough, headache, chills, weakness, runny nose, number infected in household

*Minimum and maximum possible values will also be used for imputing the following:* Daycare Days Missed, Work Days Missed, number infected in household

**Combining results from imputed datasets for nonparametric tests** For the main analysis of the primary outcome (Mantel-Haenszel test), the chi-square test statistic ( $S$ ) will be calculated for each imputed dataset. We will also calculate the MH odds ratio (MHOR), defined so that  $\text{MHOR} < 1$  suggests that Arm A has a lower rate of the outcome. If  $\text{MHOR} < 1$ ,

then let  $z = -\sqrt{S}$ . Otherwise,  $z = \sqrt{S}$ . The standard error of  $z$  is 1. If the calculated  $z$ s are the same among all of the imputations, then the final p-value is that common p-value, and the z-statistic is the common  $z$ . If the calculated  $z$ s differ, then the z-statistic will be estimated and the corresponding p-value (testing  $z = 0$ ) will be calculated using the imputation-specific  $z$ s and standard errors using SAS PROC MIANALYZE.

For the analysis of continuous outcomes using the Van Elteren test, a similar approach will be used. Instead of odds ratios, the mean in each group will be used to determine the direction of the difference. For example, if the mean of Arm A is less than that of B, then  $z = -\sqrt{S}$ , where  $S$  is the Van Elteren chi-square statistic.

**Number of imputations** We will impute and analyze 10 datasets. We will increase that number if the efficiency of the imputed datasets is less than 0.99.

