### 7.2.2 Additional Analyses of Primary Outcome

A secondary analysis of the primary outcome will test for treatment effect on the primary outcome using a logistic regression model with baseline MVS as a covariate. We will also analyze the MVS outcome as a continuous variable. For this analysis, treatment groups will be compared using a Van Elteren test, stratified by center and duration of symptoms.

We will perform further analyses of the MVS score outcomes by assessing the treatment effect after adjustment for covariates. The covariates that will be included have been described previously. A logistic regression model will be used for the indicator outcome of moderate-severe disease ( $MVS \geq 9$ ). Linear models will be used for the continuous MVS score. These models will be evaluated and adjustments will be made if any assumptions appear to be seriously violated. For example, a distribution other than the normal distribution may be used for the MVS score.

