## 7.3 Analysis of Secondary Outcomes

### 7.3.1 Duration of Symptoms, Missed Daycare and Missed Work

Duration of diarrhea, duration of vomiting (components of the MVS), days of missed daycare, and hours of missed work will be analyzed in a similar manner. Groups will be compared using the Van Elteren test, stratified by center and duration of symptoms (pre-enrollment). Analysis of duration of vomiting, missed daycare, and days of missed work will be restricted to the populations in which the measures are applicable. Additional analyses involving these outcomes will include linear regression models that adjust for possible effects of baseline characteristics.

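### The sign of each Van Elteren z comes from arm means instead of ranks, so results pooled over imputations can cancel or point the wrong way

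*Combined protocol and SAP*

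**What the plan says.** SAP v1.2 section 7.2.1 explains how nonparametric tests are combined over imputed datasets. For the primary Mantel-Haenszel (MH) test, the square root of the chi-square S in each dataset is given a sign from the MH odds ratio ("We will also calculate the MH odds ratio (MHOR"). The signed z is assigned a standard error of 1, and the imputation-specific values are pooled with their "standard errors using SAS PROC MIANALYZE". If all z values are identical, the common p-value is used.

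For continuous outcomes the same scheme is applied with a different sign rule: "Instead of odds ratios, the mean in each group will be used to determine the direction of the difference". The SAP's illustration is "For example, if the mean of Arm A is less than that of B, then" z = −√S, with S the Van Elteren chi-square. On the number of imputations it says: "We will impute and analyze 10 datasets", with more if efficiency is below 0.99.

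The Van Elteren test is used for symptom durations and missed daycare and work in section 7.3.1 ("Groups will be compared using the Van Elteren test, stratified by center and duration of symptoms (pre-enrollment"), for the numeric MVS in section 7.2.2 ("treatment groups will be compared using a Van Elteren test, stratified by center and duration of symptoms"), and for continuous tertiary outcomes in section 7.5.

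**The concern.** S measures a difference in ranks within strata. The sign attached to it comes from arm means, and the SAP mentions neither ranking nor stratification for those means. With long upper tails, a few children can move a mean without moving the ranks, so an arm can be lower by rank and higher by mean. Section 5.2 keeps valid extreme values, and section 7.6 treats missed days as counts needing negative binomial models, so skew is to be expected.

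Two kinds of error follow. If the sign is wrong in every imputation, the p-value stands but the reported direction is opposite to that of the test. If the sign differs between imputations of the same trial, values near +z and −z are averaged. The pooled z shrinks, and Rubin's rules read the sign changes as imputation uncertainty.

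Diarrhea duration, vomiting duration, missed daycare and missed work are four of the six outcomes in the Holm procedure (section 5.4). A p-value lost there can also stop the step-down for the others.

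**Working it through.** **Inputs.** From the SAP: m = 10 and standard error 1 (7.2.1); strata of center by symptom duration (7.2.2, 7.3.1); 900 children (3.3, 6.1); equal allocation (3.1); 10% loss to follow-up (3.3); two weeks of follow-up, 14 × 24 = 336 h. The documents give no distribution for durations or missed days, no number of strata and no expected imputed fraction. These are assumptions below. The pooling rule states no figure of its own to reproduce.

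**Step 1: why the MH rule is safe.** In one stratum let arm A have a events and b non-events, arm B have c and d, and n = a + b + c + d. The test numerator sums a − E(a) = a − (a+b)(a+c)/n = (ad − bc)/n. The odds ratio is Σ(ad/n) / Σ(bc/n), which is below 1 exactly when Σ(ad − bc)/n is negative. The two signs always agree.

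**Step 2: why the Van Elteren rule is not.** The numerator is Σ wₖ[Rₖ − mₖ(nₖ+1)/2], with Rₖ the rank sum and mₖ the number of arm A children in stratum k, nₖ the stratum size and wₖ = 1/(nₖ+1). No identity links its sign to that of a difference in arm means.

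**Step 3: cancellation.** Take |z| = 2.5 in all ten datasets. With B the between-imputation variance, T = 1 + (1 + 1/10)B = 1 + 1.1B, and the mean z over √T is referred to a t distribution.

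| Wrong signs | Mean z | B | T | p |
|---|---|---|---|---|
| 0 | 2.5 | 0 | 1 | 0.012 |
| 1 | 2.0 | 2.50 | 3.75 | 0.32 |
| 2 | 1.5 | 4.44 | 5.89 | 0.55 |
| 5 | 0 | 6.94 | 8.64 | 1.0 |
| 10 | −2.5 | 0 | 1 | 0.012, direction reversed |

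For one wrong sign: mean z = (9 × 2.5 − 2.5)/10 = 2.0 and T = 1 + 1.1 × 2.5 = 3.75.

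**Step 4: stratified simulation.** 900 children, 20 strata, 5% or 10% missing at random, imputation by within-arm resampling, m = 10, values capped at 336 h, 250 trials per setting, test at 0.05. Durations are lognormal. In the crossing case, log-mean and log-SD are 3.68 and 1.15 (active) against 3.90 and 0.90. In the long-tail case, active is shifted down by 0.28 on the log scale, but 8% of its children have 200 to 336 h. Missed days are negative binomial with means 1.6 and 2.0 and the same dispersion. Entries are percentages at 5% / 10% missing.

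| Case | Signs disagree (imputations) | Reject, rank sign | Reject, SAP sign | Significance lost | Significant but reversed |
|---|---|---|---|---|---|
| Null | 20 / 18 | 4.8 / 4.0 | 4.8 / 4.0 | 0 / 0 | 0 / 0 |
| Plain shift | 0.7 / 0.4 | 90 / 85 | 90 / 85 | 0 / 0 | 0 / 0 |
| Crossing | 33 / 33 | 86 / 82 | 64 / 57 | 22 / 25 | 11 / 7 |
| Long tail | 74 / 68 | 89 / 86 | 68 / 55 | 20 / 32 | 54 / 38 |
| Missed days | 1.9 / 1.4 | 57 / 48 | 57 / 48 | 0 / 0 | 0 / 0 |

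The last two columns are percentages of all trials. The Monte Carlo standard error of a proportion near 0.6 is √(0.6 × 0.4/250) ≈ 0.03.

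**Step 5: milder duration cases.** A second simulation used 450 per arm, 10% imputed, m = 10, 1,500 trials, and an unstratified Wilcoxon test as a stand-in.

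| Medians (h); log-SD | Rank sign | SAP sign |
|---|---|---|
| 43 vs 50; 1.0 vs 0.8 | 0.65 | 0.38 |
| 42 vs 50; 0.95 vs 0.85 | 0.78 | 0.75 |
| 42 vs 50; equal spread | 0.76 | 0.76 |
| Null | 0.048 | 0.048 |

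In the first row, signs were mixed across imputations in 38% of trials and the direction was reversed in 10% of significant results. A separate repeat gave 0.64 vs 0.38 for the first row and 0.81 vs 0.75 for the second. It also gave 0.64 vs 0.37 for missed-day counts whose dispersion differs between arms.

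**The case against.** The strongest reply is that the large losses need special conditions. In the 43 vs 50 h case the capped population means are about 67 and 68 h, so the mean-based sign is close to a coin toss by construction. Nothing in the documents suggests that the probiotic would shorten the median and widen the spread to that degree. This stands as a limit on how often the problem arises.

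The numeric MVS is bounded at 20 points and has no long tail. Simulated scores gave the same power under both rules (about 0.80 to 0.82), mixed signs in under 1% of trials and no reversals. This also stands. Negative binomial missed days with equal dispersion show no loss, but the case with differing dispersion does, so counts are not immune.

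The simulations may overstate sign mixing. Section 7.2.1 leaves children with no MVS data out of the imputation and bounds the imputed values, so 10% is probably too high. With an assumed bound of ±48 h and 5% imputed, the 43 vs 50 h case shows 0.66 vs 0.59 with mixed signs in 11% of trials; without bounds at 10%, the same check gave 0.60 vs 0.38 and 35%. The loss shrinks but does not vanish, and reversals remain.

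Section 7.3.1 does not mention imputation, so use of the rule for secondary outcomes is partly inferred. But section 7.2.1 refers to continuous outcomes in general and sets imputation bounds for missed daycare and work days, which supports that reading.

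Finally, one can argue that when means and ranks conflict, the direction depends on what is being estimated. That does not rescue a rule that combines the size of one measure with the sign of the other.

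**Conclusion.** The concern holds: the sign rule is wrong as written. It carries a step that is exact for the MH test over to a test where it is not, and no section checks that the mean and rank directions agree. The damage runs from none (plain shift) through about 3 percentage points of power (mild difference in spread) to 20 to 32 points, with reversed directions, where distributions cross or one arm has a long tail.

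These sizes rest on assumed distributions, strata and missingness, and on tests at 0.05 without the Holm thresholds. The sign mismatch and the cancellation arithmetic do not depend on those assumptions. The primary analysis is untouched, and type I error stayed at 4% to 5%. The exposed results are the duration outcomes first, then missed days. It should be corrected but does not threaten the trial's main conclusion.

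**What to change.** In section 7.2.1, replace the mean-based rule for the Van Elteren test with one that takes the sign of z, in every imputed dataset, from the statistic itself: the sign of Σ wₖ[Rₖ − mₖ(nₖ+1)/2] for arm A, as defined in step 2. Then pool as already planned. Equivalently, pool the signed standardized statistic directly.

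This takes one sentence in the SAP and one line of code, and it has no downside: where mean and rank directions agree, the result is identical. It should be fixed before unblinding, so that no choice of sign is made after the results are known. It would also help to say in section 7.3.1 whether the secondary outcomes are analyzed on the imputed datasets.

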### 7.2.2 Additional Analyses of Primary Outcome

A secondary analysis of the primary outcome will test for treatment effect on the primary outcome using a logistic regression model with baseline MVS as a covariate. We will also analyze the MVS outcome as a continuous variable. For this analysis, treatment groups will be compared using a Van Elteren test, stratified by center and duration of symptoms.

We will perform further analyses of the MVS score outcomes by assessing the treatment effect after adjustment for covariates. The covariates that will be included have been described previously. A logistic regression model will be used for the indicator outcome of moderate-severe disease ( $MVS \geq 9$ ). Linear models will be used for the continuous MVS score. These models will be evaluated and adjustments will be made if any assumptions appear to be seriously violated. For example, a distribution other than the normal distribution may be used for the MVS score.

### 7.2.3 Sensitivity Analysis of Primary Outcome

The daily surveys are intended to be completed on or very shortly after the corresponding study day. In some cases, a family may be contacted long after the events in question occurred. In theory, this information should have been recorded real-time in a diary. Also, there is little reason to believe the delayed information would differ in quality by treatment arm. However, we will perform a sensitivity analysis to ascertain whether the primary results hold when information collected after long delay is excluded. For this analysis, we will exclude any patient with a daily survey collected more than 14 days after the day corresponding to the survey and we will repeat the primary analysis.

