### 3.4 Follow Up Data Collection

Successful follow up will be maximized by obtaining multiple phone numbers for families and emergency contacts, scheduling calls and sending phone text reminders, allowing for electronic completion and centralizing all follow-up procedures at the lead institution (Washington University). Trained, experienced study staff will contact the family daily (including weekends) until both the diarrhea and vomiting have resolved and the treatment has been completed on day 5. Additional contact will be made on day 14 for outcome assessment, and months 1, 3, 6, 9 and 12 for long term safety outcomes. Study staff will use a standardized data collection form, and will inquire about ongoing symptoms, medical evaluations, treatments, child care, work absenteeism, and side effects. Detailed questioning will follow positive responses. A study diary will be provided to caregivers to use as a note-taking tool. Caregivers may also be provided an option of completing the follow-up collection electronically. Patient compliance with study drug administration will be assessed on day 5. To maximize compliance, caregivers will be reminded of the importance and method of administering the study drug. On day 14, the study site staff (not the central staff conducting the follow up) will perform a chart review for final data collection and identification of recorded adverse events during the 14 day study period. Adverse event reporting is described in detail in Section 8.3 on page 33.

Every effort will be made complete daily follow-up on the day necessary. However, if one or two days of follow-up contact is missed, data for those missed days may be collected on the next contact, if the caregiver used the home diaries or can recall the information. If all contact is missed but then the parent is contacted on day 14, follow-up data for the daily calls will be collected only if the parent diaries were used. For day 5 and 14, contact may be made within + 3 days. For month 1, 3, 6, 9, and 12 follow-up, contact may be made within  $\pm 2$  weeks.

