## 7.2 Analysis of Primary Outcome

The primary outcome for the study is a post-enrollment (2-week) modified Vesikari Score (MVS), defined as  $MVS \geq 9$ . The scientific hypotheses regarding the primary outcome are described in Section 3.3.

The post-enrollment score is calculated based on the elements of the score collected Day 1 through Day 14, or when symptoms resolve. Resolution of symptoms is defined as the first

Points	0	1	2	3
Diarrhea duration	0	1–96 hrs	97–120 hrs	≥ 121 hrs
Max # of diarrheal stools/24 hrs	0	1–3	4–5	≥ 6
Vomiting duration	0	1–24 hrs	25–48 hrs	≥ 49 hrs
Max # of vomiting episodes/24 hrs	0	1	2–4	≥ 5
Max recorded fever	≤ 37°C	37.1–38.4°C	38.5–38.9°C	≥ 39°C
Unscheduled healthcare visit	0	—	Primary Care	Emergency Department
Treatment	None	Rehydration	Hospital Admission	—

Table 1: Modified Vesikari Score

daily survey with absence of both diarrhea and vomiting. Each of the seven components will be assigned a score for the entire study period (from randomization to day 14). Scoring of each component is described in Table 1.

The components will be calculated by the following rules:

- 1. Maximum number of episodes of vomiting in a 24-hour period.** The number of episodes of vomiting is not collected precisely in 24-hour blocks. However, this component will be defined as the maximum number of vomiting episodes reported on a single daily follow-up survey.
- 2. Maximum number of episodes of diarrhea in a 24-hour period.** This will use the same procedure as the previous component.
- 3. Maximum temperature.** This will also use the same procedure as the two above.

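### The late-survey sensitivity analysis in SAP 7.2.3 drops whole children although its aim is to drop late information, and it can select on illness length

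*Combined protocol and SAP*

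**What the plan says.** SAP 7.2.3, added in V1.2, sets out to learn "whether the primary results hold when information collected after long delay is excluded". Its rule is that "we will exclude any patient with a daily survey collected more than 14 days after the day corresponding to the survey", after which the primary analysis is repeated. It adds that "there is little reason to believe the delayed information would differ in quality by treatment arm". It gives no expected rate of late surveys and no expected number of exclusions.

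Protocol 3.4 fixes how many surveys a child has: staff "contact the family daily (including weekends) until both the diarrhea and vomiting have resolved and the treatment has been completed on day 5". After one or two missed days, "data for those missed days may be collected on the next contact". On timing, "For day 5 and 14, contact may be made within + 3 days".

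SAP 7.2 ties the outcome to the same surveys: "The post-enrollment score is calculated based on the elements of the score collected Day 1 through Day 14, or when symptoms resolve". SAP 7.2.1 imputes missing MVS components and bounds the duration, frequency and temperature components by their minimum and maximum possible values. Children with no MVS data at all are not imputed.

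**The concern.** The unit removed is wider than the aim. One survey collected 15 days late takes out a child whose other surveys were all on time, although SAP 7.2.1 could use those surveys.

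The trigger is also a post-randomization variable that can be related to the outcome. A child ill beyond day 5 has more surveys, so more opportunities for one to be late, and longer diarrhea scores more MVS points. If the result changed, one could not tell whether recall, a changed case mix or lost precision was responsible. What is at stake is the interpretability of one supportive analysis.

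**Working it through.** **Inputs from the documents.** 25% versus 15%, two-sided alpha 0.05, 90% power, total 670 (SAP 3.3); equal allocation (SAP 3.1); about five surveys for every child, more only if symptoms persist (protocol 3.4); score period to day 14 (SAP 7.2). **Assumed, because the documents give nothing:** the late rate per survey, its clustering within a child, and survey counts by outcome.

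**The plan's own figure.** Pooled formula without continuity correction: n per arm = [1.960·√(2·0.20·0.80) + 1.282·√(0.25·0.75 + 0.15·0.85)]² / 0.10² = 334.2, so 335 per arm and 670 in total. This reproduces the plan.

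**Chance of exclusion, independent lateness.** P = 1 − (1 − p)^k for k surveys.

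| Late rate p | k = 5 | k = 8 | k = 14 |
|---|---|---|---|
| 1% | 4.9% | 7.7% | 13.1% |
| 2% | 9.6% | 14.9% | 24.6% |
| 5% | 22.6% | 33.7% | 51.2% |

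The 14-to-5 ratio is 2.3 to 2.7. The share of surveys lost is about 4.5 to 13 times the share that is late.

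**Clustered lateness.** A beta-binomial with p of 2% to 5% and intra-child correlation 0.3, 0.6 and 0.9 gives 14-to-5 ratios of about 1.6, 1.3 and 1.1. Lost-to-late ratios fall to 2.9–4.8, 1.9–2.6 and 1.2–1.3.

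**One catch-up contact.** A survey for day d collected on day T trips the rule if T − d > 14. On day 14 or 15 none does; on day 16 only day 1; on day 17, the end of the window, only days 1 and 2. Every child has those surveys, so illness length plays no part. A survey for day 6 or later trips the rule only if collected on day 21 or later.

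**Effect on the result, near-worst case.** Give every non-event 5 surveys and every event 9 (p = 2%) or 12 (p = 3%).

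- p = 2%: retention is 0.98^5 = 0.904 for non-events and 0.98^9 = 0.834 for events. Placebo rate: 0.25·0.834 / (0.25·0.834 + 0.75·0.904) = 23.5%. Active rate: 14.0%. Difference 9.5 points; about 11% of children lost.
- p = 3%: retention is 0.97^5 = 0.859 and 0.97^12 = 0.694. Rates are 21.2% and 12.5%. Difference 8.7 points; about 17% lost.

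The rule thus drops 17% to 31% of events and 10% to 14% of non-events.

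**Overlapping illness lengths, p = 2%.** With 70% of events and 30% of non-events having 8 surveys, and the rest 5, the difference is 9.9 points. With 80% and 30% having 10 surveys, it is 9.7.

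**Odds ratio.** Both arms' odds are multiplied by the same retention ratio, which cancels: (0.15/0.85)/(0.25/0.75) = 0.529 before and after exclusion in all these scenarios.

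**Power on 670.** Assumed late rates of 1%, 2% and 5% exclude about 6–7%, 12–13% and 27–30% of children, and power becomes about 0.86–0.88, 0.82–0.86 and 0.65–0.78. The lower ends take all events at 14 surveys and all non-events at 5.

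**The case against.** The strongest reply is that this is a conventional restriction check. Each child contributes one binary outcome from a score calculated once; if any maximum or duration in it rests on a late survey, dropping that outcome is simple and transparent. Imputing instead adds reliance on a model, and if all of a family's surveys are late it changes almost nothing. This is fair, and is why the exclusion should stay as an additional check.

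The second reply is that the gradient is not a documented fact. Every child has about five surveys whatever happens before day 5. SAP 7.2.3 itself pictures a family reached long afterwards, which suggests clustering. Events need not be long illnesses: vomiting of 49 hours or more (3), five or more vomits (3), six or more stools (3) and diarrhea under 97 hours (1) make 10 points with illness over by day 4. All this stands, and it limits the gradient to a possibility.

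A reader might infer that the rule biases the treatment comparison. The documents do not support that: selection on outcome that is equal in both arms leaves the odds ratio and the null test intact. Equality is not guaranteed, since treatment might shorten illness and so reduce survey counts. Even so, if events on active had one fewer survey each and non-events were unchanged, the odds ratio would move only by a factor 1/(1 − p), about 1.02 to 1.05 for p of 2% to 5%.

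**Conclusion.** The mismatch between aim and rule follows from the text of SAP 7.2.3 and needs no assumption. Preferential removal of longer illness is conditional: it requires early surveys to arrive on time and later ones to be late, with little clustering. The losses calculated above illustrate that condition; they are not forecasts, because late rate, clustering and survey counts by outcome are all assumed.

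Two stronger conclusions are tempting and unsupported. One is that the analysis necessarily loses far more data than is late; the multiple runs from about 1.2 to 13 depending on clustering that the documents do not give. The other is that the trial's main result is at risk; the primary intention-to-treat analysis keeps these children and no decision rule depends on this check. The point is a modest one about a supportive analysis, worth correcting because a survey-level version can be built on methods already in the plan.

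**What to change.** In SAP 7.2.3:

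1. Set to missing only the surveys collected more than 14 days after their study day. Also set to missing any imputation predictors known solely from those late contacts, such as time to symptom resolution or days of daycare and work missed.
2. Impute the MVS components under SAP 7.2.1, letting the on-time surveys supply the bounds, and repeat the primary test on all randomized children who still have some MVS data. Children with none stay missing, as 7.2.1 already provides.
3. Keep the patient-level exclusion as an extra check.
4. Report the number of late surveys and of children affected or excluded, by arm and outcome, so that a reader can see whether selection occurred.

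The cost is SAP wording, one more imputation run, and reliance on the imputation model for the affected children.
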